7.2.7. Concomitant therapy

7.2.7.1. The patient will provide a list of medications taken within 4 weeks prior to enrollment, and will provide a new list during each clinic visit while being treated with axitinib. The name, dose, date of start, date of stop (if use for short term), indication of the medication will be listed. (Appendix J)

7.2.7.2. The patient should not start a new prescription medication or over-the-counter medication before consulting with the study investigator, except in the case of a medical emergency.

7.2.7.3. No other cancer/investigational therapies should be started during the current study without consulting with the study investigator.

7.2.8. Treatment intake monitoring

7.2.8.1. The patient will be provided with a pill diary to record date of treatment, day of treatment, time of treatment, dose. Missed doses will be recorded as well. (Appendix J)

7.2.8.2. Pill counting. The patient will bring the axitinib bottle(s) when coming for a clinical visit. Pills will be counted by nurse/provider and recorded on a CRF and medical records.

7.2.8.3. Unused or expired axitinib pills will be disposed per MDACC institutional policy.

7.2.9. Treatment Start-Eligible patients will start treatment within 4 weeks of enrollment.

7.2.10. A history, physical examination, medication list (Appendix J), ECOG Performance Status, Adverse Events, FKSI-15 questionnaire (Appendix E) will be performed and recorded in the medical record and appropriate CRFs on weeks 3, 7, and 12. An EKG will be performed and the results recorded in the medical record and appropriate CRFs on weeks 3 and 12.

- 7.2.11. Laboratory studies that include CBC, CMP, PT, PTT, UA will be obtained prior to starting axitinib, then at week 3, week 7, and week 12 after starting axitinib. In addition, blood studies for TSH, free T3, and free T4 will be performed prior to starting axitinib, and then blood studies for TSH will be performed at week 3, week 7, and week 12 after starting axitinib. With each blood draw, 4 tubes of research blood will be drawn and processed for DNA, serum, plasma, and PBMC isolation for correlative studies, after the patient has provided informed consent.
- 7.2.12. Imaging: CT scans of the chest and abdomen (renal protocol) will be obtained on week 7 and week 12 of therapy. Patients with evidence of disease progression by RECIST version 1.0 at week 7 (primary or metastatic) will be considered treatment failures and their axitinib treatment will be permanently discontinued. Subsequently, their surgery will be performed earlier than initially planned. The urologist (investigator assessment) and the radiologist (independent assessment) will perform the tumor measurements. Response will be determined by the radiologist assessment. Tumor measurements will be documented in the tumor measurement form (one of the CRFs) and medical record.
- 7.2.13. Surgery: Following successful completion of presurgical therapy, patients will undergo radical nephrectomy (open or laparoscopic at the surgeon's discretion), with retroperitoneal lymph node dissection. Extent of lymph node dissection will be recorded in the operative record and should include the ipsilateral nodes from renal hilum to aortic bifurcation, as well as the interaortocaval nodes from renal hilum to aortic bifurcation. Primary tumor specimens will be immediately sent to pathology on ice for further processing and correlative study specimen harvest. Routine perioperative parameters will be recorded and will include operative approach, operative time, estimated blood loss, ease of surgical dissection, comment on tissue planes, intraoperative complications (with grade), post-operative complications (with grade), blood transfusions, length of ICU stay (if applicable), length of hospital stay, perioperative mortality (within 30 days of surgery). The operating urologist will make a decision based on their extensive surgical expertise if these adverse events are attributable to axitinib or not. These events will certainly be monitored and recorded by the operating urologist, and discussed with the IND if they arise.

7.3. Post-treatment follow-up

- 7.3.1. Patients will be seen at week 19 (+/- 1 week) and evaluated with CT chest and abdomen (renal protocol), full laboratory analysis (CBC, CMP), collection of blood and urine for research, and full history and physical examination. Evidence of disease recurrence [If a patient develops any evidence of biopsy-proven RCC after axitinib/surgery (in the form of local disease or distant disease), the patient will be labeled as having disease recurrence] or treatment related morbidity will be recorded. Pathology will be reviewed and will be assessed for histology, Fuhrman grade, percentage tumor viability, pathologic tumor size, presence of venous, extracapsular, sinus, or nodal involvement.
- 7.3.2. A history, physical examination, medication list (Appendix J), ECOG Performance Status, Adverse Events, FKSI-15 questionnaire (Appendix E) will be performed and recorded in the medical record and appropriate CRFs on week 19.
- 7.3.3. Patients will be followed with similar evaluations every 4 months (+/- 2 weeks) for the first year, then every 6 months (+/- 2 weeks) for the next 2 years, , then yearly (+/- 1 month) until year 5 postoperatively. Evidence of recurrence or treatment related morbidity will be recorded.

8. Tissue, Blood, and Urine Banking

- 8.1. Tissue-Kidney biopsy specimen and kidney surgical specimen will be collected
 - 8.1.1. Kidney biopsy specimen. A total of 4 adequate biopsy cores are needed. Each core should undergo touch prep by cytopathologist to ensure biopsy quality (ie, malignant cell present with minimal necrosis/hemorrhage). More cores will be obtained if touch prep shows inadequate diagnosis (to obtain a total of 4 adequate cores).
 - 8.1.1.1. One core will be fixed for pathologic evaluation and sent for pathology department for review prior to starting treatment.
 - 8.1.1.2. Three cores will be immediately placed in 3 separate cryotubes, labeled appropriately, and stored at -70° to -80°C for future use.
 - 8.1.1.3. All 4 touch prep slides will be labeled appropriately, and stored at room temperature for future use.
 - 8.1.2. Kidney surgical specimen:
 - 8.1.2.1. Tissues from final kidney surgical specimen (4 pieces of tumor, 5-10mm diameter each; and 4 pieces of normal appearing kidney cortex, 5-10mm diameter each) will

be collected in the pathology department. Each piece will be placed in a separate cryotube, labeled appropriately, and stored at -70° to -80°C for future use.

8.1.2.2. In accordance with pathology standards, several blocks of tissue will be fixed in formalin and embedded in paraffin, and stored at room temperature for future use.

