4.2. Secondary Objectives

- 4.2.1. Study the safety, tolerability, and feasibility of Axitinib in patients with locally advanced biopsy-proven clear cell renal cell carcinoma prior to undergoing radical nephrectomy.
- 4.2.2. Assess disease-free survival and overall survival in patients with locally advanced biopsy proven clear cell renal cell carcinoma treated with 12 weeks of neoadjuvant Axitinib followed by radical nephrectomy.
- 4.2.3. Collect renal tissue, blood (serum, plasma, DNA, and PBMC), and urine for future correlative biomarker studies.

5. Assessment of Response

CT scans of the chest and abdomen will be evaluated by a urologist and an expert genitourinary radiologist. The urologist (investigator assessment) and the radiologist (independent assessment) will perform the tumor measurements. Response will be determined by the radiologist assessment. Tumor measurements will be documented in the tumor measurement form (one of the CRFs) and medical record. GURU will be used as electronic case report forms (CRF). RECIST version 1.0 criteria will be used as follows to quantify response to therapy:

- Complete Response (CR): Complete disappearance of renal mass.
- Partial Response (PR): At least a 30% decrease in the largest diameter (LD) of the renal mass taking as reference the baseline largest diameter.
- Progressive disease (PD): At least a 20% increase in the LD of the renal mass taking as reference the LD of the renal mass recorded since the treatment started. PD will also include development of any biopsy-proven metastatic disease.
- Stable Disease (SD): Neither sufficient shrinkage to qualify for PR nor sufficient increase to qualify for PD taking as reference the LD since the treatment started.
- Objective response rate (ORR) is defined as CR+PR.
- ORR will be evaluated when CT abdomen is done after 12 weeks of treatment (see Table 4).
- PD will be evaluated when CT abdomen is done after 7 weeks and 12 weeks of treatment (see Table 4).

6. Statistical Considerations

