6.2. Statistical Considerations for Secondary Objectives

- 6.2.1. To examine the safety of axitinib, we will tabulate reported adverse events (adverse events will be recorded per CTCAE v4.0).
- 6.2.2. To examine the tolerability of axitinib, we will use the FKSI-15 (Functional Assessment of Cancer Therapy-Kidney Specific Index-15, Appendix E) questionnaire and compare changes in response between different time points.
- 6.2.3. We will evaluate disease-free survival by plotting Kaplan-Meier curves and estimating median recurrence-free survival. Time to death or recurrence will be defined as the time from treatment start until death, recurrence or progressive disease, whichever comes first. Patients who did not die, recur or have progressive disease will be censored at date of last follow-up. These will be compared to contemporary, matched (2:1 matching, for age group, stage and grade), historical controls. Although small differences in recurrence-free and overall survival might not be detected in this current trial, this information will help us when designing future large trials with this particular agent.

7. Treatment Plan (Table 4)

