7.2.6.1. Axitinib dose increase: Because previous studies indicated variable drug levels in patients, the axitinib dose will be increased in a step-wise fashion from 5 mg twice daily to 7 mg twice daily, then to 10 mg twice daily, in the absence of axitinib-related toxicity greater than or equal to grade 2 for a continuous 2-week period and in the absence of hypertension (defined as two blood pressure [BP] measurements of > 150/90 mmHg taken in the clinic > 1 hour apart) at any point during study. The clinical judgment of the treating physician should be exercised in up-titrating the axitinib dose.

7.2.6.2. Axitinib dose modifications for adverse events (other than hypertension and proteinuria):

7.2.6.2.1. Patients developing axitinib-related CTCAE Grade 1 adverse events may have their dose increased to next dose level.

- 7.2.6.2.2. Patients developing axitinib-related CTCAE Grade 2 adverse events should have their dose continued at the same dose level.
- 7.2.6.2.3. Patients developing axitinib-related CTCAE Grade ≥ 3 adverse events should have their dose reduced as indicated in section 7.2.6.2.6
- 7.2.6.2.4. If patients need to have their axitinib treatment interrupted for 2 or more continued-week period due to unmanageable toxicities or any other reason, their axitinib treatment will be permanently discontinued and considered treatment failures. Patients will then proceed to surgery to have their kidney tumors removed.
- 7.2.6.2.5. Patients removed from treatment for intolerable toxicity should still be followed with regular tumor assessments (every 4 months for 1 year, every 6 months for the next 2 years and every 12 months for one more year) until disease progression or start of new treatment, and for survival thereafter until study completion.
- 7.2.6.2.6. The criteria for dose modification for study-drug-related adverse events are summarized in the table below:

CRITERIA FOR DOSE MODIFICATION FOR AXITINIB-RELATED ADVERSE EVENTS OTHER THAN HYPERTENSION OR PROTEINURIA	
Related Adverse Events	INTERVENTION
Grade 1	Increase to next dose level, or maintain if already at the maximum dose
Grade 2	Continue at same dose level
Grade 3 nonhematologic treatment-related toxicity* or Grade 3 hematologic toxicity	Decrease dose to one lower dose level

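### Recurrence after nephrectomy is defined only through biopsy, so disease-free survival is overstated to the extent that CT-evident recurrences go unbiopsied in living patients

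*Combined protocol and SAP*

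**What the plan says.** Section 7.3.1 defines recurrence by this condition: "If a patient develops any evidence of biopsy-proven RCC after axitinib/surgery (in the form of local disease or distant disease"). When it is met, "the patient will be labeled as having disease recurrence". Section 7.3.3 extends follow-up to year 5 after surgery and says "Evidence of recurrence or treatment related morbidity will be recorded", without a second definition.

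Section 6.2.3 builds the endpoint on this: "Time to death or recurrence will be defined as the time from treatment start until death, recurrence or progressive disease, whichever comes first". Everyone else is handled by one rule: "Patients who did not die, recur or have progressive disease will be censored at date of last follow-up".

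Section 5 defines progressive disease as "At least a 20% increase in the LD of the renal mass", and adds "PD will also include development of any biopsy-proven metastatic disease".

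Table 4 schedules CT of chest and abdomen at every follow-up visit and marks percutaneous biopsy at pre-treatment only. For patients taken off axitinib for toxicity, Sections 7.2.6.2.5, 7.2.6.3.5 and 7.2.6.4.4 continue tumor assessments "until disease progression or start of new treatment, and for survival thereafter until study completion".

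**The concern.** Follow-up detects disease by CT, but the DFS event depends on a tissue diagnosis that no section requires. A patient whose scan shows clear new metastases, and who is treated on that basis, has no event under the plan's wording and keeps accruing disease-free time.

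DFS is a named secondary objective. Section 6.2.3 compares it with 2:1 matched historical controls and intends the result to inform the design of later, larger trials. With 24 patients, one or two misclassified events can visibly move the curve. The plan does not say how recurrence is established in the controls, so the two groups may be measured by different rules.

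**Working it through.** The documents state no DFS rate, event count or power, so there is no figure to reproduce. The check has two parts.

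**1. Can imaging-only recurrence become an event after nephrectomy?**

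- *Recurrence (7.3.1):* biopsy-proven disease, local or distant. No imaging or clinical alternative is given, and 7.3.3 adds none.
- *Progressive disease, primary tumor (Section 5):* growth of the renal mass. The mass has been removed.
- *Progressive disease, metastatic (Section 5):* biopsy-proven.
- *RECIST progression (7.2.12):* applies to the week 7 scan on treatment.
- *Start of new treatment (6.2.3):* neither an event nor a censoring point.
- *Death (6.2.3):* an event, so a missed recurrence is counted late if the patient dies during follow-up.

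The only remaining outcomes for an unbiopsied recurrence are death or censoring at last follow-up.

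**2. How large could the effect be?** All inputs except the sample size are assumptions.

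- Patients: 24 (Section 6.1).
- True 5-year DFS: 60%, with exponential recurrence. Hazard λ = −ln(0.60)/5 = 0.1022 per year.
- Survival after recurrence: exponential with a 3-year median. Hazard μ = ln 2/3 = 0.2310 per year.
- Share of recurrences never biopsied: u = 10%, 25% or 40%.
- No death without recurrence, and all survivors followed to 5 years.

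Labelled DFS(5) = true DFS(5) + u × A, where A is the probability of having recurred and being alive at 5 years:

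A = λ × (e^(−5λ) − e^(−5μ)) / (μ − λ) = 0.1022 × (0.600 − 0.315) / 0.1289 = 0.226.

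If nobody dies after recurrence, A = 1 − 0.60 = 0.40, which is the ceiling.

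| Unbiopsied share u | Excess, 3-year median survival | Patients of 24 | Excess, no deaths | Patients of 24 |
|---|---|---|---|---|
| 0% | 0 | 0 | 0 | 0 |
| 10% | 2.3 points | 0.5 | 4 points | 1.0 |
| 25% | 5.6 points | 1.4 | 10 points | 2.4 |
| 40% | 9.0 points | 2.2 | 16 points | 3.8 |

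With 5-year recurrence varied from 30% to 50%, u from 10% to 30%, and post-recurrence survival from a 2-year median to no deaths, the excess runs from 1.4 to 15 points (0.3 to 3.6 of 24 patients). For scale, the standard error of a 60% proportion in 24 patients is √(0.60 × 0.40/24) = 0.10, or 10 points.

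**The case against.** The best defense is that biopsy proof is a deliberate choice. Section 5 and Section 7.3.1 both use it, and it keeps indeterminate CT findings from counting as events. Section 7.3.1 says *if*, not *only if*, and 7.3.3 records recurrence without repeating the biopsy condition. A for-cause biopsy would not normally appear in a visit schedule, so its absence after surgery in Table 4 is weak evidence that none would be done. DFS is secondary, carries no success threshold, and Section 6.2.3 itself concedes that small differences may go undetected.

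Much of this stands. It limits the size and weight of the point but does not supply a second route to an event: an analyst following the text has no basis for counting an unbiopsied recurrence. The protection against false-positive scans is real and can be kept in a sensitivity analysis.

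Three stronger readings are tempting, and the documents do not support them:

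- *DFS will certainly be overstated, by up to 16 points.* No section says that suspicious lesions go unbiopsied, and the 4, 10 and 16 point figures ignore deaths, which Section 6.2.3 counts as events.
- *Censoring adds a second upward bias.* Section 6.2.3 does not censor at new treatment, and 7.3.3 continues evaluation to year 5, so this is largely the same missed event. The switch to survival-only contact is written for patients removed for toxicity, and the plan does not define last follow-up.
- *The comparison favors axitinib.* That would follow if control recurrences were taken from imaging or charts without biopsy. The plan does not say how they are found.

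**Conclusion.** The point holds as a gap in the DFS event definition. As written, a living patient with an unbiopsied recurrence after nephrectomy is counted as disease-free. The direction is upward whenever this occurs. The size cannot be determined from the documents because the unbiopsied share is not given. Under the stated assumptions it is about 2 to 9 points at 5 years, bounded by 4 to 16 points with no deaths after recurrence, and zero if every recurrence is biopsied. In most of these scenarios it is smaller than the sampling error of about 10 points, but it is systematic and avoidable.

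The comparison with controls is biased if their recurrences are ascertained by a different rule; the plan sets none, so the direction of that bias is unknown. Only the secondary DFS endpoint is affected. The objective response criterion, the stopping rules and overall survival are untouched.

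**What to change.** In Sections 7.3.1 and 6.2.3, for the DFS analysis:

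- Define recurrence as the first of biopsy-proven RCC, unequivocal new or growing disease on the scheduled CT, or start of treatment for recurrent RCC.
- Date the event at the first imaging evidence.
- Apply the same definition and dating to the matched historical controls.
- Censor event-free patients at their last tumor assessment instead of an undefined last follow-up.
- Report DFS with biopsy-proven recurrence only as a sensitivity analysis.

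The cost is wording in two sections, with no added patient procedure because the CTs are already scheduled. There is some extra work: someone must make the imaging call through year 5, and control records must be read against the same rule. Section 5 already names a radiologist for the response assessments. The statistical downside is an occasional false-positive CT event, which the sensitivity analysis would expose.

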8.2. Blood

8.2.1. Four different tubes will be collected at specified visits (Table 4), processed, labeled appropriately, and stored in aliquots at -70° to -80°C for future use.

8.2.1.1. Tube 1 (8cc): PAXgene Blood DNA tube to collect DNA

8.2.1.2. Tube 2 (8cc): BD Vacutainer CPT tube to collect plasma (Sodium Citrate) and PBMC

8.2.1.3. Tube 3 (10cc): BD Vacutainer EDTA tube to collect plasma (K2 EDTA) and PBMC

8.2.1.4. Tube 4 (10cc): BD Vacutainer Serum tube to collect serum

8.3. Urine

8.3.1. 30-50cc fresh voided urine obtained will be collected at specified visits (Table 4), processed, labeled appropriately, and stored in aliquots at -70° to -80°C for future use.

8.4. Blood and urine collection for research are optional but extremely valuable for the study. These samples will be used in the future to study predictors of response to therapy with axitinib.

9. Good Clinical Practice

9.1. Informed Consent:

The investigator/team will explain to the patient the nature of the clinical trial, its goal, potential benefits and risks. The patient will be informed that participation in the trial is voluntary, and that withdrawal is allowed at any time of the study, and that withdrawal will not affect subsequent medical treatment or relation with treating investigator/team. The informed consent is a document written in non-technical language. The patient will need to read the consent, ask pertinent questions, sign and date prior to starting study treatment. Separate consents will be obtained for required preoperative biopsy.

9.2. Institutional Review Board (IRB):

Prior to enrolling the first patient in this study, the protocol, related documents, and the informed consent forms will be reviewed by the Departmental Research Committee, the Clinical Research Committee, and the IRB. Pertinent amendments to the protocol will need to be approved by the IRB and the IND Sponsor – IND Office.

9.3. Ethical Conduct of Study

This study will be conducted according to GCP, US 21 Code of Federal Regulations (CFR) Part 50 (Protection of Human Subjects); US 21 CFR Part 56 (IRBs); US 21 CFR Part 54 (Financial Disclosure); International Conference on Harmonization (ICH) Guidance for Industry, E6 GCP: Consolidated Guidance; the Nuremberg Code; and, where applicable, the 1996 version of the Declaration of Helsinki (World Medical Association Declaration of Helsinki, 1996).

9.4. Patient Confidentiality:

All information collected during the study will be recorded in case report forms (CRF) and placed in a patient-specific folder. The information in the CRFs will then be put into a research database at M.D. Anderson Cancer Center. This database will identify the patient by a study number. The study number will be assigned by the research nurse, and all subsequent research records will contain the study number only. The link between the study number and patient identifiers will be kept in a limited access database with password protection. The informed consent will be kept in the medical record. The research records will be kept in the research nurse office at M.D. Anderson Cancer Center, and will be accessible to the Principal Investigator, the collaborators, and the research staff as designated by the Principal Investigator. Strict adherence to HIPAA regulations will be maintained at all times. The research subject will not be identified in any reports on this study. The results will be identified by the patient's study number. Only authorized personnel such as members of the University of Texas M.D. Anderson Cancer Center Institutional review board, Principal Investigator, Co-Investigators, collaborators, and research staff will be allowed to access the data. Data [abdominal CT scans, age, gender, race, height, weight, body mass index, serum albumin (both before and after treatment with axitinib), serum total protein (both before and after treatment with axitinib), current disease status, response to axitinib treatment, complications related to axitinib treatment or surgery, performance status, pathologic tumor stage, pathologic tumor grade, and tumor size] from this study may also be shared and used in protocol PA15-0949.

Table 4. Summary of protocol studies

Studies	Pre-treatment*	W1	W3	W5	W7	W9	W12	W13	W19 (±1w)	Q4M x 1Y (±2w)	Q6M x 2Y (±2w)	Q12M X 2Y (±1M)	
History & Physical	X		X		X		X		X	X	X	X	
Medication list	X	X	X		X		X		X	X	X	X	
ECOG PS	X	X	X		X		X		X	X	X	X	
FKSI-15 ¹		X	X		X		X		X	X			
Adverse Events	X		X		X		X		X	X	X	X	
Nurse phone call ²				X		X							
Informed consent	X												
EKG	X		X				X						
Routine labs													
CBC	X		X		X		X		X	X	X	X	
CMP ³	X		X		X		X		X	X	X	X	
PT, PTT	X		X		X		X						
TSH	X		X		X		X						
Free T3, free T4	X												
Urinalysis	X		X		X		X						
Pregnancy test (urine or serum)	X	X											
Study blood [#]													
PAXgene DNA	X ⁴		X		X		X		X	X	X	X	
Red top	X ⁴		X		X		X		X	X	X	X	
Purple top	X ⁴		X		X		X		X	X	X	X	
CPT	X ⁴		X		X		X		X	X	X	X	
Study urine [#]	X ⁴		X		X		X		X	X	X	X	
Imaging													
CT chest	X				X		X		X	X	X	X	
CT abdomen	X				X		X		X	X	X	X	
MRI brain ⁵	X ⁵												
Bone scan ⁶	X ⁶												
Pathology													
Percutaneous biopsy	X												
Final pathology								X					
Nephrectomy								X					
Axitinib		-----X-----											

*Evaluations need to be completed within 4 weeks of study enrollment

[#]Blood and urine collection for research are optional but extremely valuable for the study. These samples will be used in the future to study predictors of response to therapy with axitinib

¹ FKSI-15, Functional Assessment of Cancer Therapy-Kidney Specific Index-15 (Appendix E)

² Nurse phone call will mainly assess adverse events and BP measurements

³ CMP includes sodium, potassium, chloride, carbon dioxide, calcium, glucose, BUN, creatinine, magnesium, phosphorus, lactate dehydrogenase, AST, ALT, alkaline phosphatase, total and direct bilirubin, albumin, total protein

⁴ The blood samples for research can be drawn on W1-prior to first intake of axitinib-if it was not drawn at enrollment

⁵ If CNS symptoms are noted

⁶ If alkaline phosphatase is abnormal or if bone pain is present

W=week, M=month, Y=year, Q=every

References:

